1.3 Schema

The general study design is shown in Figure 1.

Lipo.dox=pegylated liposomal doxorubicin.

2 INTRODUCTION

Study D9170C00001 is a Phase I/IIa, open-label, multi-centre, study of AZD7648 administered orally, either as monotherapy, or in combination with either cytotoxic chemotherapies or novel anti-cancer agents to patients with advanced malignancies. The modular design allows the evaluation of the safety, tolerability, and preliminary efficacy of multiple study treatments. The Core Module will investigate AZD7648 as a monotherapy, and Combination Module 1 will investigate AZD7648 administered in combination with pegylated liposomal doxorubicin (PLD).

Details related to study rationale, background and benefit/risk assessment for Combination Module 1 can be found in Section 11 (see Section 4.1.1 for further details on the modular structure).

cancer cells, UU
. Such instability results in an accumulation of CCI
CCI
. CCI
vitro and in vivo systems CC

2.1 Study rationale

2.2 Background

DNA damage events occur frequently in any living cell and various mechanisms have evolved to deal with them. Different forms of DNA damage trigger responses by different repair mechanisms and signalling pathways (Figure 2).

Among DNA damage lesions, DSBs are the most cytotoxic. They induce cell cycle arrest and cell death if left unrepaired. NHEJ pathway of DSB repair occurs independently but is preferentially used during the early G1/S phases, where no template sister chromatid is available (Hartlerode and Scully 2009). This contrasts with the second major pathway of DSB repair, homologous recombination (HR), which occurs primarily in G2/M phases of the cell cycle when undamaged sister chromatids are available (San Filippo et al 2008).

DNA-PK is a member of the phosphatidylinositol 3-kinase-related kinase (PIKK) family (that includes ataxia telangiectasia mutated [ATM] and ATR) and is a key modulator for the NHEJ

pathway of DNA repair elicited by DSBs (Jackson et al 1993) and for V(D)J recombination, a process that utilises NHEJ to promote immune system diversity (Blunt et al 1995).

DNA-PK is activated when it is recruited to DSBs by Ku70/80 heterodimer. Autophosphorylation of the DNA-dependent protein kinase catalytic subunit (DNA-PKcs), is critical for the regulation of DNA-end processing, enzyme inactivation, and complex dissociation (Chan et al 2002). Activated DNA-PKcs promotes DNA-end tethering (Graham et al 2016) which prevents DNA degradation by exonucleases (Yoo and Dynan 1999) and alters the activity of a wide range of substrates that mediate DNA-end processing and resolution (Figure 3) (Neal and Meek 2011).

DNA-PK has also been implicated in a range of other biological processes, including modulation of chromatin structure, telomere maintenance, transcriptional regulation, and the response to replication stress (Figure 4) (Goodwin and Knudsen 2014).

Type of damage: Single-strand Double-strand breaks Bulky adducts Nucleotide e.g. from platinum breaks (SSBs) (DSBs) mutations, and UV substitutions. deletions, insertions **Repair targets:** APE1 ERCC1 MLH, MSH, ATR ATM **DNA-PK** XP proteins MTH1*, etc PARP Polymerases **Base Excision** Non-Homologous Nucleotide MisMatch Repair **Repair pathway:** Homologous Recombination **Excision Repair** Repair End Joining and TransLesion Repair **Synthesis** Damaging agent(s): RTx RTx **RTx** UV light Replication errors Topo I inhibitors Alkylating agents Topo II inhibitors Platinum agents Alkylating agents Nucleoside analogue Platinum potentiation but The most dNTP sanitation* **Rationale for targeting:** The most cytotoxic lesion safety concern over common lesion **UV** sensitization

Figure 2 DNA damage repair pathways including non-homologous end joining pathway

DNA-dependent protein kinase (DNA-PK) adds non-homologous end joining (NHEJ) repair targeting to the DNA damage response agent (DDR) portfolio. APE1=apurinic/apyrimidinic endonuclease; ATM=ataxia telangiectasia mutated; ATR=ataxia telangiectasia and Rad3-related protein; PARP=poly ADP ribose polymerase; RTx=treatment; UV=ultraviolet; XP=xeroderma pigmentosum.

Figure 4

Phosphorylation of H2AX at DNA double-strand breaks (DSB) and auto-phosphorylation of DNA-dependent protein kinase catalytic subunit (DNA-PKcs) S2056 during non-homologous end joining (NHEJ) repair.

Role of DNA-PK in replication stress response

Phosphorylation of RPA32 by DNA-dependent protein kinase (DNA-PK) during replication stress response. Adapted from O'Connor 2015. Upregulation of DNA-PK has been reported in various tumour types, correlates with poor clinical prognosis, and has been shown to correlate with decreased response to DNA damaging agents and therapeutic resistance in multiple cancers, such as colorectal cancer, oesophageal cancer, oral squamous cell carcinoma, and neuroblastoma (Goodwin and Knudsen 2014, Shintani et al 2003, Hosoi et al 2004, Shintani et al 2003, Tonotsuka et al 2006, Dolman et al 2015, Beskow et al 2009).

The concept of targeting DNA-PK as an anti-cancer strategy is based on exploiting tumour dependence on NHEJ repair. Synthetic lethal interactions have been identified between DNA-PK and multiple damage response factors including ATM and HR proteins suggesting that a DNA-PK inhibitor may show efficacy as monotherapy in specifically selected genetic backgrounds (Gurley et al 2001, Oken et al 1982, Riabinska et al 2013, Dietlein et al 201). Furthermore, combining a DNA-PK inhibitor with agents that increase levels of DNA DSBs in cells – such as radiation, topoisomerase 2 inhibitors (eg, doxorubicin) represents another rational strategy for clinical development of DNA-PK inhibitor.

There is currently one other DNA-PK selective inhibitor, M3814, known to be undergoing clinical trials. A Phase I study (NCT02316197) of M3814 showed that the drug was safe and tolerable at doses up to 400 mg BID with limited single-agent activity (Van Bussel et al 2017) and a Phase Ia/b study is now being conducted in combination with radiation and chemoradiation (NCT02516813). Preliminary results from 16 patients dosed across 3 cohorts (100 mg, 200 mg, and 400 mg once daily [QD]) in combination with radiation have shown that the combination was well tolerated, although some Grade 3 events of mucositis and odynophagia were observed. Two dose-limiting toxicities (DLTs) were observed at 400 mg QD therefore 300 mg QD is being explored. Initial efficacy data from 12 evaluable patients was reported to have 1 complete response (CR), 4 partial responses (PR) and 7 stable disease (SD) (Van Triest et al 2018). Two additional studies are also recruiting patients: a Phase I study (NCT03724890) to evaluate RP2D and/or MTD of M3814 in combination with avelumab with and without radiotherapy in solid tumours; and a Phase Ib/2 study (NCT03770689) to first define RP2D of M3814 in combination with capecitabine and radiotherapy followed by evaluation of the combination efficacy in patients with locally advanced rectal cancer. There are 2 other DNA-PK drugs, SF-1126 and CC-115, in Phase I clinical trials but, unlike AZD7648 and M3814, they are known to be multi-kinase inhibitor and dual-kinase inhibitor respectively.

A detailed description of the chemistry, pharmacology, efficacy, and safety of AZD7648 is provided in the Investigator's Brochure (IB).

2.3 Benefit/risk assessment

The Core Module of the study is a first time in human (FTIH) Phase I/IIa dose escalation study with the DNA-PK inhibitor AZD7648. Detailed information about the known and

expected benefits and risks of AZD7648 may be found in the IB. The study design aims to minimise potential risks and although the potential benefits in patients are unknown at this time, non-clinical data demonstrates evidence of anti-tumour activity. Thus, the benefit/risk assessment for this Phase I/IIa study appears acceptable based on the lack of effective alternative treatments, the limited life expectancy due to malignant disease, and the strength of the scientific hypothesis under evaluation.

3 OBJECTIVES AND ENDPOINTS

Primary objective:	Endpoint/Variable:							
To investigate the safety and tolerability of AZD7648	Adverse events (AEs)/serious adverse events (SAEs)							
when given orally to patients with advanced	DLTs							
malignancies, as monotherapy and in combination	Physical examination							
with anti-cancer agents, and define the doses and schedules for further clinical evaluation	Eastern Cooperative Oncology Group performance status (ECOG PS)							
	Vital signs							
	Electrocardiogram (ECG) and Echocardiogram							
	(ECHO; Combination Module 1 only)							
	Laboratory data							
Secondary objectives:	Endpoint/Variable:							
To characterise the PK of AZD7648, following a single dose and at steady state after multiple dosing, when given orally as monotherapy and in combination with anti-cancer agents. To characterise the effect of food on AZD7648 exposure (if conducted)	Area under the curve (AUC) and/or AUC_{0-t} after a single dose and AUC_{tau} after multiple doses. Maximum plasma concentration (C_{max}) after a single dose and $C_{max,ss}$ after multiple doses Time to reach maximum plasma concentration (t_{max}) Minimum plasma concentration at steady state ($C_{min,ss}$) Half-life ($t_{1/2}$)							
	Dose proportionality							
	AUC _{0-t} and C _{max} ratio for food effect							
To understand the cytochrome P450 3A4 (CYP3A4) induction potential of AZD7648	Post-dose to pre-dose 4-β-hydroxy cholesterol ratio							
To obtain a preliminary assessment of anti-tumour	Radiological response evaluated using response							
activity of AZD7648 as monotherapy and in	evaluation criteria in solid tumours (RECIST) 1.1							
combination with anti-cancer agents	• Percentage best change in target lesion (TL)							
	Duration of response							
	• Objective response rate (ORR)							
	• Progression-free survival (PFS)							
	• Overall Survival (OS) (Part B only)							

Table 2Study objectives

Tertiary/Exploratory objectives:	Endpoint/Variable:
	CCI
CCI	CCI CCI CCI
CCI	CCI

4 STUDY DESIGN

4.1 Overall design

This is a modular Phase I/IIa, open-label, multi-centre, study of AZD7648 administered orally, either as monotherapy, or in combination with either cytotoxic chemotherapies or novel anti-cancer agents to patients with advanced malignancies. The modular design allows for an escalation of the dose of AZD7648 alone or in combination with either cytotoxic chemotherapies or novel anti-cancer agents, with intensive safety monitoring to ensure the safety of the patients.

For an overview of the study design see Figure 1, Section 1.3. For study flow charts and details of treatments given during the Core Module and Combination Module 1 see Sections 6.1, and 14.1, respectively.

For details on what is included in the safety, efficacy and exploratory endpoints, see Section 3 Objectives and Endpoints (applicable to the Core Module and Combination Module 1).

4.1.1 Modular protocol structure

The structure of the protocol will follow a modular design.

The initial module will be a Core Module relating to AZD7648 monotherapy. Additional combination modules may be added as described below, via a formal amendment, based on emerging supportive preclinical data and study rationale. The decision to initiate a combination module once regulatory approvals have been obtained will be made by the SRC. The starting dose/schedule of AZD7648 in further combination modules will not exceed the equivalent maximum exposure of AZD7648 found to be tolerated in the core module or from other studies in the clinical programme at that point.

List of Modules

The following starting modules for the study are included within this protocol.

- 1 **Core Module**: AZD7648 Monotherapy. Part A, dose escalation (which may include a food effect cohort)
- 2 **Combination Module 1**: AZD7648 + PLD. Part A, dose escalation and Part B, safety and PoC Phase IIa expansions
- 3 Up to 5 additional combination modules may be added as follows:
 - Combination with a DDR agent eg, ATR inhibitor
 - Combination with an immuno-oncology agent eg, PD-L1 inhibitor
 - Combination with a cytotoxic agent eg, paclitaxel
 - Combination with an antibody-drug conjugate

• Combination with radiotherapy/radiation therapy

The maximum number of modules in this protocol will be eight, inclusive of the Core Module. The modular protocol structure is shown in Figure 5.

AE=adverse event; PK=pharmacokinetic; PLD=pegylated liposomal doxorubicin.

4.1.2 Core module study design: AZD7648 monotherapy

This part of the study is dose escalation (Part A) of AZD7648 monotherapy, administered orally, in approximately 46 evaluable patients with advanced solid tumours. Further details of the study design for Combination Module 1 can be found in Section 12.

The starting dose of AZD7648 is	mg CCI. A single dose of A	AZD7648 will be administered
during CCI	. Fro	om Cycle 1, Day 1, the initial
schedule will be AZD7648 dosed	on a continuous basis in a C	Cl . There will be no
interval between cycles. Using an	accelerated titration design	(see Table 4), dose escalation
may occur with single patient coh	orts up to and including ^{CCI} n	ng CCI From ^{CCI} mg CCI

onwards, a minimum of 3 patients will be enrolled into each dose cohort. Dose escalation will stop at the maximum tolerated dose (MTD), maximum feasible dose (MFD), or the RP2D.

Dose escalations with single patient cohorts may proceed up to and including \square mg \square following SRC recommendation (informed by real-time PK analysis) and provided no CTCAE Grade ≥ 2 drug-related toxicity is observed. If either of these conditions is not met, the cohort will be expanded to recruit a minimum of 3 patients (maximum of 6 patients) in all subsequent cohorts. At this point, the decision to dose escalate AZD7648 will follow the principles of the Bayesian adaptive design, using all of the available data and considering the PK from a minimum of 2 out of the 3 patients enrolled into each dose cohort (data from all evaluable patients will be used to make the dose escalation decision). The DLT period is from the first dose until the end of Cycle 1 (inclusive of any non-dosing days). This DLT assessment period was selected as the major potential toxicities would be anticipated to present within this duration. Doses and/or schedules of AZD7648 will be defined by the SRC by taking the Bayesian adaptive design and PK into consideration.

Part A cohorts may be expanded at doses at or above the monotherapy Minimum Biologically Active Dose (MBAD) in parallel to continuing the dose escalation cohorts provided the dose has already been declared as tolerated. Further recruitment to such an expansion cohort will stop if the dose in that cohort is subsequently evaluated to be non-tolerated. The optional expansion cohort(s) are described in Section 6.1.2.1.

Escalation will stop at the MTD, MFD, or the RP2D.

To account for the dose range between starting dose and target dose level, intra-patient dose escalation is permitted as part of the monotherapy dose escalation to maximise patient benefit and minimise exposure to non-efficacious doses. However, the following criteria must be fulfilled before a patient is permitted to proceed with an intra-patient dose escalation:

- The planned next higher dose must be declared tolerated by the SRC (based on assessment of 2 to 6 evaluable patients).
- Agreement by the SRC that the patient is permitted to have an intra-patient dose escalation.
- Intra-patient dose escalation occurs on Day 1 following a scheduled scan assessment.

Whilst a patient is being considered for an intra-patient dose escalation, they should continue treatment at their allocated dose level. In the event of an intra-patient dose escalation, such patients will not be evaluable for DLT at the escalated dose.

No Part B expansion is planned in the Core Module but there are optional expansion options as described in Section 6.1.2.1.

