Combination Module 1 has 2 study parts: Part A consisting of dose escalation cohorts and Part B, a safety and proof of concept (PoC) Phase IIa expansion. Part A dose escalation and de-escalation will follow the principles of the Bayesian adaptive design which combines prior expectations about the dose toxicity relationship and applies the data at the end of each cohort to recommend a dose for the next cohort. A Safety Review Committee (SRC) will review evaluable patients at each cohort and assess if the study should progress to Part B. Optional expansion cohorts may also be triggered in Part A dose escalations, enrolling additional patients at appropriate dose(s) to explore further the safety, tolerability, pharmacodynamics (PD), pharmacokinetics (PK), biological activity and effect of food.

Main Objectives:

The primary objective is to investigate the safety and tolerability of AZD7648 when given orally to patients with advanced malignancies, as monotherapy and in combination with anti-cancer agents, and to define the doses and schedules for further clinical evaluation.

Secondary objectives are i) to characterise the PK of AZD7648, following a single dose and at steady state after multiple doses, when given orally as monotherapy and in combination with anti-cancer agents, and to characterise the effect of food on AZD7648 exposure (if conducted); ii) to obtain a preliminary assessment of anti-tumour activity of AZD7648 as monotherapy and in combination with anti-cancer agents.

Tertiary/exploratory objectives are described in Section 3.

Study Period:

Estimated date of first patient enrolled: Q4 2019

Estimated date of last patient completed: Q2 2024

Number of Patients:

Approximately 192 evaluable patients may be enrolled in the Core Module (95 evaluable patients: 46 patients in the dose escalation and up to 49 additional patients in optional expansion cohorts) and Combination Module 1 (97 evaluable patients: 30 patients in the dose escalation with the potential for an additional 30 patients once maximum tolerate dose [MTD] has been determined, and 37 patients in the expansion cohort).

Treatments and Treatment Duration:

For the Core Module, a single dose of AZD7648 will be administered in the clinic (Cycle 0, Day 1) to enable collection of blood samples for PK analyses. This will be followed by a drug washout (no dose) of 3 to 7 days prior to Cycle 1, Day 1 AZD7648 administration.

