6.1.3 Definition of dose-limiting toxicity

DLTs will be evaluated during Cycle 0 and Cycle 1 of treatment. Toxicity will be graded according to the National Cancer Institute CTCAE v5.0.

A DLT is defined as an AE that occurs from the first dose of study treatment up to and including Cycle 1, Day 28 (the DLT assessment period) that is assessed as unrelated to the disease, intercurrent illness, or concomitant medications and that, despite optimal therapeutic interventions, meets any of the following criteria:

Haematological Toxicities:

- Grade 4 neutropenia lasting > 4 days.
- Grade 4 thrombocytopenia.
- Grade \geq 3 neutropenia (ANC < 1000 cells/mm³ [< 1 x 10⁹/L]) of any duration accompanied by fever \geq 38.5°C and/or systemic infection.
- Grade \geq 3 thrombocytopenia (< 50,000/mm³ [< 50 x 10⁹/L]) with bleeding.

Non-haematological Toxicity CTCAE Grade ≥3 Including:

- Confirmed laboratory abnormalities greater than 72 hours of duration.
- Nausea or vomiting for more than 3 consecutive days despite administration of maximal anti-emetic therapy.
- Diarrhoea for more than 3 consecutive days despite administration of maximal anti-diarrhoeal therapy.
- QTc prolongation > 500 milliseconds or QTcF prolongation from baseline by 60 milliseconds confirmed on at least 2 separate ECGs.
- Any other toxicity that is greater than that at baseline AND is clinically significant and/or unacceptable, and does not respond to optimal therapeutic intervention within 72 hours AND is judged to be a DLT by the SRC.
- Any treatment-related event, including significant dose reductions, omissions or delays, judged to be a DLT by the SRC. Examples may include CTCAE Grade 2 toxicities that are clinically significant and/or unacceptable according to the Investigator, toxicities that result in an inability to administer at least 75% of study treatment during Cycle 1 or delay the administration of study treatment in the subsequent cycle by ≥ 7 consecutive days.

DLT Will not Include the Following:

- Transient isolated laboratory abnormalities which are not considered clinically significant and resolve to baseline within 72 hours without any intervention.
- Alopecia.
- Toxicity unrelated to treatment eg, related to the underlying disease or disease-related process under investigation.
- Grade 4 vomiting and diarrhoea lasting < 72 hours in the absence of maximal medical therapy.

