8.4.5 Management of IP-related toxicities

Details of DLTs can be found in Section 6.6.

8.5 **Pharmacokinetics**

Venous blood samples (2 mL) for determination of concentrations of AZD7648 and the potential metabolites (if any) in plasma will be taken at times presented in Table 10. Samples will be split to provide plasma for the primary analysis and secondary/backup analyses. The backup sample may be used for the metabolite identification work. Blood and urine samples for PK analysis will be collected as specified below (Table 10) and in the SoA (Table 1).

Full details of sample handling procedures, storage and shipping will be provided in the lab manual. The date and time of collection of each sample will be recorded.

Urine samples (~10 mL) for the determination of AZD7648 concentration will be taken from the total urine sample provided during each of the collection intervals. The date and time of collection and the volume of each total urine collection will be recorded. Approximately 50 mL of the urine sample may also be used to identify metabolites, if any.

Results will only be reported for samples shipped within a timeframe for which the stability of AZD7648 in the samples has been validated and shown to be acceptable.

All patients start with a single dose of AZD7648 to fully profile the PK of AZD7648, followed by an approximately 3 to 7 day washout. If the half-life of AZD7648 is shorter than expected the washout period can be shortened or may not be required at all.

Pharmacokinetic samples will be taken at the times indicated in Table 10.

 Table 10
 AZD7648 PK sample collection schedule in monotherapy cohorts

	Blood	Urine
Cycle 0, Day 1	Pre-dose, and 15 minutes (min), 30 min, 60 min, 2 hours (h), 4 h, 8 h, 10 h to12 h post-dose	Pre-dose, and 0 to 8 h, 8 to 24 h post-dose
Cycle 0, Day 2	24 h post-dose	
Cycle 0, Day 3	48 h post-dose	
Cycle 0, Day 4	72 h post-dose	
Cycle 1, Day 1	Pre-dose	
Cycle 1, Day 8 (or Visit Y for intermittent schedules)	Pre-dose, and 15 min, 30 min, 60 min, 2 h, 4 h, 8 h, 10 to12 h post-dose	0 to 8 h, 8 to 24 h post-dose note: urine not requited at Visit Y

	Blood	Urine
Cycle 2, Day 1	Pre-dose	
Cycle 3, Day 1	Pre-dose	
Cycle X, Day 1 (if a patient has a dose escalation to another dose, then, at the time of escalation); this provides the starting exposure at the time of escalation	Pre-dose and 1 h post-dose	

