9.4 Statistical analyses

The statistical analyses will be performed by Parexel or other designated third-party providers, under the direction of the Biostatistics Group, AstraZeneca. Further detail will be provided in the Statistical Analysis Plan (SAP).

Data from each part/module will be presented separately. All patients who undergo intra-patient dose escalation will be analysed & reported as per their starting dose.

Methods common to all modules are detailed below.

Demographic Data

Characteristics of the patients, including medical history and disease characteristics at baseline will be listed for each patient and summarised by cohort.

Reasons for discontinuation of study treatment will be listed including the study day of treatment discontinuation and will be summarised by cohort.

Exposure

Exposure to each study treatment, ie, total amount of study treatment received will be listed for all patients.

Total treatment duration (=date of last dose minus date of first dose + 1) and actual treatment duration (=total treatment duration excluding dose interruptions not in accordance with the protocol) will be summarised for each study treatment and cohort by the following: mean, standard deviation, minimum, maximum, median, and number of observations. In addition, the number and percentage of patients with at least 1 non-protocolled dose interruption and at least 1 dose reduction will be presented separately for the initial period of evaluability defined as 28 days and for any time following this initial period of the study.

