The reference date for all assessments except for tumour assessments, will be the start of the study treatment in cycle 0 (i.e., cycle 0, day 1). There is no study day 0 for this study. Date of cycle 1, day 1 dosing will be considered as the start date for the calculation of efficacy endpoints (tumour response, PFS), which follows CSP visit window starting from cycle 1, day 1. The study day will be displayed in the data listings. If an event starts before the reference start date, the study day displayed on the listing will be negative.

Time Windows

Time windows will need defining for any presentations that summarise values by visit.

Given the washout period between Cycle 0 and Cycle 1 can vary between patients (3-7 days per CSP) and therefore study day of Cycle 1 Day 1 onwards will vary, for the purposes of windowing assessments the study day of visits from Cycle 1 Day 1 onwards will be adjusted in order to allow the same window to be applied across patients. This will not impact on study day displayed in listings and will be used only by programming as an intermediate step to assign analysis visits. The amount to adjust the study day by will be derived assuming the planned day for Cycle 1 Day 1 is day 8 for all patients:

Adjustment (days) = 8 – actual Cycle 1 Day 1 study day

Study day for all safety assessments from Cycle 1 Day 1 onwards will be adjusted by this amount when assigning assessments to analysis visits. Actual, unadjusted study day will be presented in listings.

The following conventions should apply:

- Inclusion within the time window should be based on the actual date and not the intended date of the visit.
- The visit window following baseline will be constructed as per [Table 4](#) for the safety assessments
- For summaries showing the maximum or minimum values, the maximum/minimum value recorded on treatment will be used (regardless of where it falls in an interval).
- Listings should display all values contributing to a time point for a patient.
- Often the most meaningful summaries focus on extreme values rather than summaries at each visit but if summaries over time are felt to be required:
- For visit based summaries

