3.2.1.3 Dose limiting toxicities (DLTs) and patients evaluable for DLTs

A patient will be defined as evaluable if they have completed the DLT evaluation period with sufficient dosing, at least 75% of the total amount of planned dose of AZD7648 (and PLD for combination module 1). Additionally, patients who have a DLT are considered evaluable. Patients who withdraw from the study prior to completion of the first 28 day safety observation period for reasons other than a DLT will not be considered evaluable.

At each SRC meeting, the patients in the current dose escalation cohort are reviewed by the SRC, the SRC will agree on the patients who are evaluable or have a DLT following Section 6.1.3 of the CSP. The evaluable patients will be used by the SRC to inform the next dose decision.

See Section 6.1.3 of the Clinical Study Protocol for the definition of a DLT. For reporting purposes, the DLTs and the list of DLT evaluable patients are as approved and documented at the Safety Review Committee meetings.

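### Dose interruptions and reductions are split at 28 days with no stated start date, while the DLT period runs from first dose to Cycle 1 Day 28, about 31 to 35 days

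*Protocol*

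**What the plan says.** Two protocol sections define the DLT period, and they agree. Protocol 4.1.2 has "The DLT period is from the first dose until the end of Cycle 1 (inclusive of any non-dosing days"; Protocol 6.1.3 has "from the first dose of study treatment up to and including Cycle 1, Day 28 (the DLT assessment period". In dose escalation the first dose is the single Cycle 0 dose. The Synopsis says of the core module: "This will be followed by a drug washout (no dose) of 3 to 7 days prior to Cycle 1, Day 1 AZD7648 administration". Protocol 8.5 adds that, if the half-life is shorter than expected, "the washout period can be shortened or may not be required at all".

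A 28-day period appears in three other places:

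- Protocol 9.4 (Exposure) presents the patients with at least one interruption or reduction separately for "the initial period of evaluability defined as 28 days" and for the time after it.
- SAP 4.2.1 repeats this split. Neither section gives a start date.
- SAP 3.2.1.3 first requires an evaluable patient to have completed the DLT evaluation period with sufficient dosing. It then treats as not evaluable "Patients who withdraw from the study prior to completion of the first 28 day safety observation period for reasons other than a DLT".

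On how days are counted, SAP 3.1 says: "The reference date for all assessments except for tumour assessments, will be the start of the study treatment in cycle 0".

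**The concern.** A period named for evaluability should coincide with the period over which patients are evaluated for DLTs. Here it has a different length and no origin, so the programmer must choose one. If the count starts at the Cycle 0 dose, the cut falls before Cycle 1 ends, at a point in the cycle that moves with each patient's washout. Interruptions and reductions in the last days of the DLT period would then appear as later events. That would make tolerability within the DLT period look somewhat better than it was, in a report that SAP 1.1 says focuses primarily on safety.

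**Working it through.** **Inputs.** Cycle length is 28 days (Protocol Table 1, footnote a). The washout is w = 3 to 7 days (Synopsis). Study day 1 is Cycle 0 Day 1 (SAP 3.1). For visit windowing, the SAP takes Cycle 1 Day 1 as planned on study day 8.

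**Plan's own figures first.** Treating w as days elapsed from Cycle 0 Day 1, Cycle 1 Day 1 is study day 1 + w. For w = 7 this is 1 + 7 = 8, which matches the SAP's planned day. The 28-day figure equals one cycle. It ends together with the DLT period only if it is counted from Cycle 1 Day 1.

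**Counting from first dose.** The DLT period ends on study day (1 + w) + 27 = 28 + w. Study day 28 is Cycle 1 Day 28 − w. The DLT days after the cut number (28 + w) − 28 = w.

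| w | Cycle 1 Day 1 (study day) | DLT period ends (study day) | Study day 28 is Cycle 1 Day | DLT days after the cut | Share of DLT period |
|---|---|---|---|---|---|
| 3 | 4 | 31 | 25 | 3 | 3/31 = 9.7% |
| 4 | 5 | 32 | 24 | 4 | 4/32 = 12.5% |
| 5 | 6 | 33 | 23 | 5 | 5/33 = 15.2% |
| 6 | 7 | 34 | 22 | 6 | 6/34 = 17.6% |
| 7 | 8 | 35 | 21 | 7 | 7/35 = 20.0% |

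As a share of Cycle 1, the days after the cut run from 3/28 = 10.7% to 7/28 = 25%.

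**Counting from Cycle 1 Day 1.** The 28 days end on Cycle 1 Day 28, which is study day 31 to 35. No late Cycle 1 interruption or reduction is misplaced. Only Cycle 0, one dose and a planned washout, is left out.

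**Sensitivity to the washout.**

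- If 3 to 7 means full no-dose days between the two doses, Cycle 1 Day 1 is study day 5 to 9 and the DLT period is 32 to 36 days. Then 4 to 8 days fall after the cut (4/32 = 12.5% to 8/36 = 22.2%).
- If the washout is dropped and Cycle 1 starts the day after the Cycle 0 dose, the DLT period is 29 days and 1 day falls after the cut.
- With no Cycle 0, the period is 28 days and the two definitions agree.

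**Which start date do the documents favour?** SAP 3.1 makes Cycle 0 Day 1 the general reference date, and the treatment-duration formulas in Protocol 9.4 and SAP 3.2.1.1 count from the date of first dose. Both point to first dose. Neither is stated to govern the 28-day split.

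**The case against.** The best defence is that the 28 days simply mean Cycle 1. A cycle is 28 days, Protocol 6.1.2 ties the 75% dose requirement to Cycle 1, and Cycle 0 is a single in-clinic dose with a planned washout, so there is little to interrupt. On that reading nothing late is misplaced. The SAP's reference date is also written for assessments and study day, not for this table. This stands as far as it goes: the misplacement is conditional. But the text does not say Cycle 1, and the exposure formulas beside it start from first dose.

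The consequences are also limited. Every interruption and reduction is still counted; only its period could change. Under Protocol 6.1.4 the SRC reviews exposure data, including interruptions and reductions, directly, so escalation decisions do not depend on this table. SAP version 4.0 was written after the sponsor decided to halt development. All of this stands and keeps the point small.

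A reader might go further and infer that patients observed for only part of the DLT period can count as evaluable. Take w = 7 and continuous dosing. A patient who leaves after study day 28 has completed 28 days and received 21/28 = 75% of the Cycle 1 dose, with 7 of 35 DLT days unobserved. The documents do not support the inference. SAP 3.2.1.3 opens by requiring completion of the DLT evaluation period, and this patient, without a DLT, has not completed it. The 28-day sentence adds an exclusion; escaping it does not satisfy the requirement. The DLT evaluable set is also taken from the SRC minutes (SAP Table 2, footnote b), so no 28-day program cut creates it. The set definitions in Protocol 9.3 and SAP Table 2 do not repeat the completion requirement, and they refer to minimum safety evaluation requirements that neither document spells out. That is loose drafting, not a rule that admits such patients.

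**Conclusion.** The point holds as a small defect in a descriptive safety table. The 28-day split in Protocol 9.4 and SAP 4.2.1 has no start date and does not match the DLT period. If counted from first dose, which the SAP's conventions favour, it ends 3 to 7 days early, on Cycle 1 Day 21 to 25. Events starting after that are then reported outside the period they belong to. If counted from Cycle 1 Day 1, there is no late misplacement.

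The range of 31 to 35 days is derived, not stated. It assumes that the washout is counted in elapsed days and is actually applied. How many events would move cannot be judged from the documents. The sentence in Protocol 4.1.2 is not at fault; it and Protocol 6.1.3 give the definition to which the other sections should be aligned.

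**What to change.** In Protocol 9.4 and SAP 4.2.1, replace the 28 days with the DLT assessment period, defined as first dose of study treatment to Cycle 1 Day 28. In SAP 3.2.1.3, replace the first 28-day safety observation period with the same term, so that its two sentences apply one period. Because this wording does not name Cycle 0, it also fits Part B of Combination Module 1, which has no Cycle 0.

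The cost is three wording changes and one programming cut-off, set by each patient's Cycle 1 Day 28. No data collection changes, and the DLT evaluable set stays as the SRC documented it.
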